2.4. Analyses

Statistical analyses will be based on the basis of international guidelines (CPMP/ICH/363/96:E9). Due to the early stop of the study, only an exploratory and descriptive analysis takes place. Statistical methods used to compare groups for primary and secondary outcomes:

Efficacy: Change of systolic 24-h ambulatory BP at 6 months post-procedure (primary efficacy endpoint) compared between the RDN and sham group will be analyzed in a linear mixed model including the covariates that were significantly different between the groups at baseline. All secondary (see 1.1.2) and observational endpoints (1.1.3 and 1.1.4) are analyzed also via a modelling approach adjusting for potential imbalances in baseline characteristics. The type I error for the analysis of the primary endpoint is set at 5% (two-sided), all analyses of secondary endpoints have an exploratory character avoiding multiplicity issues in this trial.

In addition, a win ratio analysis will be conducted, with the criteria 24h ambulatory systolic BP change > 5 mmHg, office systolic BP change > 10 mmHg, and decrease of medication as defined by following 3 parameters (number of antihypertensive drugs, drug burden index and antihypertensive load index).

Analysis will be performed for the following populations:

1. Primary analysis is based on *the intention-to-treat* (ITT) population consisting of all randomized study subjects that are all either RDN treated or sham treated.
2. A secondary analysis will be done with a *modified ITT* population (mITT) in which participants with adherence violations will be excluded (sensitivity analyses).
3. A secondary analysis will be done with the *per protocol population* (PPP) in which study subjects with predefined protocol deviations (defined prior to unblinding of the data) are excluded.
4. A secondary analysis will be done with the modified *per protocol population* (mPPP) in which study subjects of the PPP with adherence violation are excluded.
5. A secondary analysis will be done with the safety population (SAF) in which all study subjects signing informed consent are included.

6. A secondary analysis will be done with those patients that are investigated by the Erlanger and Nürnberger center (CRC staff), with a total of N=20 randomized patients (Bavarian cohort)

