1.1.1. Primary objective

The primary efficacy parameter is:

- Change in systolic 24-h ambulatory BP at 6 months post-RDN-procedure from pre-procedure (including 1. Pre-treatment value (**P**) = average of the pre-procedure visit (week -1) value and screening visit (week -4) value, 2. Baseline value (**B**) = pre-procedure visit (week -1) value only) compared *between the 2 groups* (RDN-Treatment group vs. Sham group).

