1.3. Trial Flow Sheet

Enrollment of subjects occurred at the clinical sites only after the appropriate local study approvals, “Approval to Enroll” documentation from the Sponsor and written informed consent from subjects have been obtained.

Visit #	V1	V2	V3	V4	V5	V6	V7	V8 ⁷	V9	V10
Week	-4	-1	0	3	6	12	19	26	39	52
Informed consent	X									
Inclusion/exclusion criteria	X									
Medical history	X									
RDN/Sham Procedure			X							
Physical exam	X	X	X	X	X	X	X	X	X	X
24-h ABP measurement ¹	X	X				X		X		X
Office (attended) BP ²	X	X	X	X	X	X	X	X	X	X
Safety and efficacy lab	X	X	X	X	X	X	X	X	X	X
AEs/ADEs	X	X	X	X	X	X	X	X	X	X
UACR ³ , eGFR, Cystatin C	X	X				X		X		X
Urinary toxicological analyses ⁴		X				X		X		X
Body fluid composition		X						X		X
MRA of Renal Arteries ⁵		X								
Duplex ultrasound ⁶		X								X
Medication review	X	X	X	X	X	X	X	X	X	X

Visit schedule (# all visits can be scheduled +/-5days)

- 24-h ambulatory BP measurements will be conducted by mobilograph (IEM, Aachen) allowing also the assessment of central systolic BP in addition to brachial BP readings.
- Office (attended) BP according to ESH guidelines with automated oscillometric device while nurse/physician is in the room (attended visits).
- UACR – albumin/creatinine ratio.
- To assess adherence to prescribed medication
- MRA has only to be performed if no images (previous MRI, previous CT, previous angiogram) of anatomy of renal artery supply is available
- If the last duplex sonography examination displays signs of renal artery stenosis or is not fully evaluable according to the investigator’s discretion, an angiogram needs to be performed to rule out or diagnose any renal artery abnormality which can be compared with the angiogram performed at baseline.
- Patients who will not have 12 months follow up visit until June 2023 but thereafter will have a shorter follow up period of 6 months only and unblinding will take place after all data of the 6 months FU visit have been entered and secured in the database (the rationale is that the primary objective is change in blood pressure after 6 months!

2. Outcome Measures and Target Parameters

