2.9. General Analysis

2.9.1. General Methodology

Descriptive statistics will be displayed for all documented and derived variables. For continuous variables, number of observations, number of missing values, mean, standard deviation, minimum, median and maximum will be calculated. For categorical variables, number of patients, absolute and relative frequencies will be calculated.

In this parallel, controlled study, data analysis will be performed using unadjusted analysis, i.e. simple paired and unpaired t-test under the assumption of a normal distribution for the difference of interest.

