2.9.3. Analysis of Demographic and other Baseline Characteristics

Demographic and patient characteristics will be summarized in tables and listings for the SAF, ITT, modified ITT, PPP, modified PPP, Bavarian population, separated by treatment groups and for the total population.

The demographic characteristics are: age and gender etc.

Summary of medical history and prior or concomitant medication will be presented.

The summary of medical history and current medical conditions including all previous and current medical conditions will be presented by preferred term and by body system of the system.

Baseline values of the efficacy measures will be presented in the efficacy section.

Baseline laboratory values will be presented.

Data from patients who were enrolled into the study, but not treated renal denervation or sham, will be presented in listings. No further analyses will be done with these patients' data.

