2.9.4.1. Primary efficacy variable

Primary variable is the change in systolic 24-h ambulatory BP at 6 months post-procedure compared between the 2 groups.

Hence, (e.g.) the following null hypotheses H_0 , will be tested against their alternative hypotheses H_1 using unpaired t-test:

H_0 : There is no significant difference in systolic 24-h ambulatory BP at 6 months post-renal denervation compared between the 2 groups. (RDN group vs. sham group)

H_1 : There is a significant difference in systolic 24-h ambulatory BP at 6 months post-renal denervation compared between the 2 groups (RDN group vs. sham group).

The overall significance level of the trial is defined as $\alpha = 0.05$ (two-sided).

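### Baseline 24-h systolic BP enters the primary model only if it differs significantly between arms, so it is left out in about 95% of randomisations (5% test assumed)

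*SAP*

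**What the plan says.** Section 2.4 puts the primary endpoint in a linear mixed model "including the covariates that were significantly different between the groups at baseline". That is the only covariate rule for the primary model. The level of the baseline tests is not given, and there is no list of candidate covariates. The nearest thing to a list, in 2.9.3, serves the demographic tables and is itself open-ended: "The demographic characteristics are: age and gender etc".

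Section 2.4 also says that the secondary and observational endpoints "are analyzed also via a modelling approach adjusting for potential imbalances in baseline characteristics". It names no fixed covariate for them.

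Two later sections describe a different analysis. In 2.9.1, "data analysis will be performed using unadjusted analysis, i.e. simple paired and unpaired t-test"; in 2.9.4.1 the primary hypotheses "will be tested against their alternative hypotheses H_1 using unpaired t-test". Neither brings in baseline BP except by subtracting it.

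The change is to be computed from two starting values (1.1.1): P, the "average of the pre-procedure visit (week -1) value and screening visit (week -4) value", and B, the week -1 value alone.

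**The concern.** The trial is randomised 1:1, so a baseline difference between arms is a chance event. Its p-value does not show whether the variable predicts the outcome, which is what decides whether adjustment helps. Baseline 24-h systolic BP is an obvious candidate as a predictor of 24-h systolic BP at 6 months, yet the rule admits it only in the few randomisations where the baseline test happens to be positive.

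Using a change score does not settle the matter. It subtracts baseline with a slope of 1, whereas the regression slope of the 6-month value on baseline is below 1. A chance imbalance is therefore over-corrected, and the estimate shifts against the sign of the imbalance.

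The model also cannot be known in advance. Testing baseline differences between arms needs the treatment codes, so the covariates are settled only once allocation is available, from candidates nobody has listed.

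**Working it through.** The SAP gives no power, SD, effect size or sample-size calculation, so there is no figure to reproduce.

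**Inputs from the SAP.** 1:1 randomisation (1.2); two-sided 5% for the primary test (2.4, 2.9.4.1); target of 80 patients, not reached (1.2); 20 randomised patients in the Bavarian cohort (2.4). The number randomised overall is not stated, so 40 per arm is a ceiling.

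**Assumptions, not in the SAP.** SD 12 mmHg at each visit; true effect 6 mmHg; the same correlation r between any two of week -4, week -1 and month 6, taken as 0.4, 0.6 or 0.8; a 5% baseline test; baseline BP as the only candidate covariate; 20 or 40 per arm.

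**1. How often baseline is omitted.** Under randomisation the null hypothesis of the baseline test is true, so P(omit) = 1 − level: 95% at a 5% test, 90% at 10%, 80% at 20%. Simulation gave 94.9–95.1% at 5%, whatever the sample size or correlation.

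**2. Precision.** Ratio of the variance with baseline adjustment to that of the plain change score, in large samples:
- B: (1 − r²)/[2(1 − r)] = (1 + r)/2, which is 0.70, 0.80, 0.90 for r = 0.4, 0.6, 0.8.
- P: 2(1 + 2r)/[3(1 + r)], which is 0.857, 0.917, 0.963.

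**3. Power**, from 100,000 simulated trials per cell (rule in 2.4 against baseline always included):

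| Change from | Per arm | r = 0.4 | r = 0.6 | r = 0.8 |
|---|---|---|---|---|
| B | 20 | 28.8 vs 38.1% | 40.7 vs 47.7% | 68.4 vs 71.7% |
| B | 40 | 53.0 vs 66.9% | 70.2 vs 78.4% | 94.1 vs 95.6% |
| P | 20 | 36.5 vs 40.8% | 51.4 vs 53.8% | 80.3 vs 80.8% |
| P | 40 | 64.8 vs 70.3% | 81.6 vs 84.1% | 98.1 vs 98.3% |

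**4. Shift left by an imbalance d.** The regression slope on B is r, so the change score leaves a shift of size (1 − r)d. The slope on P is 2r/(1 + r), so it leaves (1 − r)/(1 + r) × d. At r = 0.6 the fractions are 0.40 and 0.25.

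| Change from | Per arm | Median non-significant d | Shift | d at p = 0.05 | Shift |
|---|---|---|---|---|---|
| B | 20 | 2.41 | 0.96 | 7.68 | 3.07 |
| B | 40 | 1.70 | 0.68 | 5.34 | 2.14 |
| P | 20 | 2.15 | 0.54 | 6.87 | 1.72 |
| P | 40 | 1.52 | 0.38 | 4.78 | 1.19 |

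All entries are in mmHg. Example: 0.40 × 7.68 = 3.07.

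**5. Type I error.** Overall it is about 4–5% under the rule. A baseline p-value between 0.05 and 0.20 occurs in 15% of randomisations (0.20 − 0.05). There, at 20 per arm and r = 0.4, 0.6, 0.8, the error is 9.6, 8.2, 6.3% for B and 7.1, 6.7, 5.5% for P, against 4.9–5.2% with adjustment. In the 80% with p of 0.20 or more it falls below 5%: 3.2–4.4% for B and 4.1–4.9% for P.

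**The case against.** Section 2.4 calls the whole analysis exploratory and descriptive because the study stopped early, so loss of power matters less than in a confirmatory trial. The 95% is simply one minus an assumed test level and does not measure harm. For P, which the SAP lists first, the loss at r = 0.6 is about 2.5 points, and under 1 point at r = 0.8. The raised conditional error affects 15% of randomisations and is offset elsewhere. SD, effect and equal correlation are assumed, and weeks -4 and -1 lie much closer together than week -1 and month 6, so the figures for P could move either way. The simulation uses a single-visit comparison because the SAP does not specify its mixed model. If 2.9.4.1 governs, the selection rule never operates.

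Most of this is fair and limits the weight of the point. For the secondary endpoints, 2.4 names no significance test and does not rule out adjustment for the endpoint's own baseline; it only fails to fix it. The objections do not rescue the rule. The SAP still sets a two-sided 5% test for the primary endpoint, and with recruitment short of target precision is scarce. If the t-test governs, baseline is omitted every time and the variance ratios in step 2 apply in full.

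**Conclusion.** The concern holds. On either reading of the SAP, baseline 24-h systolic BP is not a planned covariate of the primary comparison. The cost is a less precise estimate and, in the one trial that was run, a shift left by any chance imbalance that misses significance. It does not cause bias over repeated randomisations or inflate overall type I error.

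Over r from 0.4 to 0.8 and 20 to 40 per arm, always adjusting gains about 1.5 to 14 points of power for change from B and 0.2 to 5.5 points for change from P. The loss is thus moderate for B and small for P. These sizes rest on the assumed SD, effect and equal correlations. The 95% rests only on randomisation and the assumed 5% baseline test. The SAP should be corrected; the point does not invalidate the trial.

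**What to change.** In 2.4, name the baseline value of the outcome as a fixed covariate whatever the baseline comparison shows: P in the change-from-P analysis and B in the change-from-B analysis. Do the same for each continuous secondary or observational endpoint with its own baseline; win-ratio and similar endpoints need their own statement. If randomisation used any factor, include it as well. Delete selection by baseline significance. Show baseline differences descriptively, and keep any imbalance-driven adjustment as a labelled sensitivity analysis. Make 2.9.1 and 2.9.4.1 name this same model as the primary test in place of the unadjusted t-test.

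The cost is wording in three sections and one degree of freedom; 24-h ambulatory BP is already scheduled at weeks -4 and -1. In the 20-patient Bavarian cohort the gain is small (r = 0.6: B 21.5 vs 25.1%, P 27.4 vs 28.4%), and for P at r = 0.8 adjusting costs about 0.4 points of power.

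Section 1.3 says, for patients with the shortened follow-up, that "unblinding will take place after all data of the 6 months FU visit have been entered and secured in the database". The SAP does not show whether that had happened. If it has, label the change post hoc.

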2.5. Computer system and Software

The statistical analysis will be performed using Statistical Analysis System SPSS (release 21 SPSS Inc. Chicago, Illinois, USA) or any other internationally accepted software (R, Python etc.) or any other internationally used statistical program that are qualified for this analysis, e.g. SAS program.

2.6. Protocol deviations and their Classification in Minor and Major

Prior to locking the trial data base, possible protocol deviations will be listed. The classification in minor or major deviations will be done at the “Blinded Data Review Meeting”. The classification into minor or major deviations will be done in cooperation between the leading investigator (LKP), the Sponsor’s Project Manager and the responsible monitoring person. Major protocol violations will be protocol deviations, which are considered to interfere with the assessments of efficacy in this trial.

2.7. Definition of Derived Variables and Transformation of Variables

2.7.1. Missing Values

Missing values in the CRF documented as “ND”, “NA” or “UNK” will usually not be entered into the database and the field will be blank.

If date parts are missing (the ‘day’ and/or the ‘month’) and there are calculations needed, a missing day will be replaced by ‘01’, a missing month will be replaced by ‘01’. A missing year will not be replaced.

In case of the start date of an AE is missing, the date of first treatment intake (if appropriate) will be used as worst case imputation, otherwise the first day/month instead of the middle will be taken also as a worst case imputation.

Data of patients having withdrawn their consent to study participation at any time point during the study were not accounted for in the respective analyses up to the time point of withdrawal.

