1.1.5. Safety analysis

- Safety endpoints and adverse effects during 3, 6 and 12 months post-procedure compared between the 2 groups (RDN-Treatment group vs. Sham group).
- Listing of AE and ADE in original term provided for each patient (Solo-Population)
Listing of SAE, AESI, SADE in original term provided for each patient
Comparison of number / percentages of SAE, AE, AESI, escape rate between the 2 groups (RDN-Treatment group vs. Sham group)
- Increase of serum creatinine / eGFR (calculated based on CKD-epi) between visit 3a (week 0) and visit 3b, and visit 3a and visit 4 (week +3) between the 2 groups (RDN-Treatment group vs. Sham group) and in each group separately

Following events will be presented at all-time points post-procedure comparing 2 groups

All-cause mortality
New onset ESRD (eGFR<15 mL/min/m ² or need for renal replacement therapy)
Significant embolic event resulting in end-organ damage
Renal artery perforation or dissection requiring an invasive intervention
Major vascular complications requiring surgical repair, interventional procedure, thrombin injection, or blood transfusion
Hospitalization for hypertensive or hypotensive crisis
Hospitalization for major cardiovascular or hemodynamic related events
New onset stroke
New onset myocardial infarction
Suspicion of new onset renal artery stenosis by renal duplex ultrasound

Following AESIs will be presented as a table at all time points post-procedure comparing 2 groups

- All-cause mortality
- Hypertensive emergency resulting in hospitalization
- Hypotensive emergency resulting in hospitalization
- Hospitalization for heart failure
- Stroke, transient ischemic attack, cerebrovascular accident
- Acute myocardial infarction (STEMI/non-STEMI)
- Any coronary revascularization
- End stage renal disease, the need for permanent renal replacement therapy (i.e. the need for dialysis); doubling of plasma creatinine, eGFR <15ml/min/1.73m²
- Any renal artery complication requiring intervention (e.g. dissection; perforation)
- Major access site complications requiring intervention
- Significant embolic events resulting in end organ damage
- Procedure-related pain lasting for > 2 days
- Acute renal injury, defined as:

- Increase in serum/plasma creatinine to ≥ 1.5 times pre-procedure visit (week -1) or decrease of eGFR (derived from creatinine, CKD-epi) by 25% known to have occurred during 7 days post procedure or
- Urine volume < 0.5 ml/kg/h for 6 hours

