- Significant ($> 50\%$) and severe ($> 70\%$) new onset renal stenosis as diagnosed by renal angiogram or CTA/MRA
- Need for renal artery angioplasty or stenting

In addition, these AESIs will also be reported as 1-month post-procedure event rates:

- Any renal artery complication requiring intervention (e.g. dissection; perforation)
- Major access site complications requiring intervention
- Significant embolic events resulting in end organ damage
- Procedure-related pain lasting for > 2 days
- Acute renal injury, defined as:
 - increase in serum/plasma creatinine to ≥ 1.5 times pre-procedure visit (week -1) or decrease of eGFR (derived from creatinine, CKD-epi) by 25% known to have occurred during 7 days post procedure or,
 - Urine volume < 0.5 ml/kg/h for 6 hours

Following major combined safety endpoint (incidence of any major adverse events (MAE) through the FU) at all time points post-procedure comparing 2 groups

- All-cause mortality
- eGFR < 15 ml/min/1.73m² or permanent need for renal replacement therapy
- Hospitalization for hypertensive crisis defined by office (attended) BP $\geq 180/110$ mmHg with clinical symptoms
- Clinical manifestation of hypertension associated target organ damage requiring hospitalization
- New renal artery stenosis $> 75\%$ as assessed by computer tomography (CT)/magnetic resonance angiography (MRA) or diagnosed/confirmed by renal angiogram
- Individual components of the combined endpoint above

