- Resolved
- Resolved with sequelae
- Ongoing
- Death

Recording and Reporting of Adverse Events

The period of observation for AEs extends from Study Screening/Baseline Eligibility Visit 1 (Week -4) until Visit 10 (Week +52). New AEs reported to the investigator during the observational period, after the study procedure must be documented, treated, and followed up like all other AEs.

AEs will not be followed up after the final investigation visit which is scheduled 12 months after the treatment with the investigational medical device.

Underlying diseases/pre-existing conditions that do not worsen during the course of the investigation are not reportable as AEs. To determine whether a condition has worsened, it is compared to the condition of the subject at baseline.

Elective treatments planned before screening and which are documented in the subject's source data are usually not regarded as AEs.

Data pertaining to AEs will be collected during each investigation visit based through the investigators inquiry or discovered in the course of examinations done during the visit. The investigators will assess and record any AE in detail in the subject file and on the CRF AE report form.

The following information were recorded:

- AE diagnosis or main symptom.
- Date of event onset.
- Severity
- Investigational medical device (blinded)
- Causal relationship (causal related, probably related, possibly related, unlikely related, not related).
- Serious (yes or no).
- Patient outcome
- Action taken /treatment.
- AE falling under the definition of an AESI (yes or no)
- AE leading to discontinuation of the investigation (yes or no)
- AE due to a device deficiency (yes/no)
- Date of event resolution

After completion of all scheduled visit assessments the investigator must document any AEs arising from these assessments. In case of an SAE, the investigator must also complete an SAE report form.

Recording and Reporting of Serious Adverse Events

All SAEs that occur during the investigation period, whether considered to be related to the investigational medical device/procedures or not, were reported by the investigator to the Sponsor within 24 hours of knowledge.

SAE report forms are provided in the ISF. Completed reports were signed by an investigator and transferred by fax to:

Medical Device Vigilance Office
Center for Clinical Studies (CCS Erlangen)
Universitätsklinikum Erlangen
[name]

[name]
[contact]
email: [contact]

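### The AE start-date rule in SAP 2.7.1 is labelled worst case but has no floor at the procedure date, so read literally it can date early post-procedure events before the procedure.

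*SAP*

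**What the plan says.** SAP section 2.7.1 (Missing Values) has two layers.

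- **General rule for incomplete dates:** "a missing day will be replaced by ‘01’, a missing month will be replaced by ‘01’. A missing year will not be replaced".
- **AE start dates, first limb:** "In case of the start date of an AE is missing, the date of first treatment intake (if appropriate) will be used as worst case".
- **AE start dates, second limb:** "otherwise the first day/month instead of the middle will be taken also as a worst case imputation".

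Three things are left open: when the first limb applies, whether it covers partly missing dates or only wholly missing ones, and what an intake is when the treatment is a single procedure at week 0.

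Two other sections determine what the rule does. Section 2.8, under recording and reporting of adverse events, says: "The period of observation for AEs extends from Study Screening/Baseline Eligibility Visit 1 (Week -4) until Visit 10 (Week +52"). Section 1.1.5 plans "Safety endpoints and adverse effects during 3, 6 and 12 months post-procedure compared between the 2 groups", and for the procedural AEs of special interest (AESIs) it adds: "In addition, these AESIs will also be reported as 1-month post-procedure event rates".

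**The concern.** Pre- and post-procedure events sit in the same data set, and the safety tables separate them by date. For a question about procedural harm, the cautious choice for an uncertain onset is on or just after the procedure. The first of the month, or 1 January, is usually earlier. Section 2.7.1 calls this choice worst case, so a programmer has no reason to question it. Because AE collection starts at week -4, a date pulled back by a couple of weeks also looks valid and would raise no query.

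At stake are the post-procedure tables at 1, 3, 6 and 12 months, above all the 1-month AESI rates. An event dated before the procedure can drop out of all of them. The target of 80 patients was not reached (section 1.2). With 1:1 allocation that means roughly fewer than 40 per arm, so one misplaced patient with an event changes an arm's rate by at least about 1/40 = 2.5 percentage points.

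**Working it through.** The SAP gives no figure on this point, so there is nothing to reproduce. The check applies the rule as written.

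**From the SAP:** missing day becomes 01 and missing month becomes January (2.7.1); AE collection starts at week -4, i.e. day -28 (2.8); tables are by time since the procedure (1.1.5).

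**Assumed, not in the SAP:** procedure dates evenly spread over a 365-day year; true onset evenly spread over days 1 to W after the procedure.

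**1. Example.** Procedure 15 June, onset 16 June.
- Day missing: 1 June, day -14, inside the AE collection period.
- Month missing: 1 January, day -165, before Visit 1.

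If onset is instead 20 September (day 97) with the day missing, the date becomes 1 September, day 78. It is earlier than the truth but still after the procedure.

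**2. Day missing, literal reading.** The event moves before the procedure only if onset is in the procedure's own month and the procedure was not on the 1st. In a month of n days, a lag of L days leaves n - 1 - L such procedure dates (none if negative).

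- W = 7: the mean lag is 4, so the mean count per month is n - 5. Over the year this is 365 - 12 × 5 = 305, and 305/365 = 83.6%.
- W of 30 or more: summing over all lags gives (n - 1)(n - 2)/2 per month, i.e. 435 for 31 days, 406 for 30 and 351 for 28. The year's total is 7 × 435 + 4 × 406 + 351 = 5,020. Dividing by 365 × W:

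| Onset window | Moved before the procedure |
|---|---|
| days 1-30 | 5,020/10,950 = 45.8% |
| days 1-90 | 5,020/32,850 = 15.3% |
| days 1-182 | 5,020/66,430 = 7.6% |
| days 1-364 | 5,020/132,860 = 3.8% |

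With 30-day months and onset allowed on day 0, the first two windows give (29 - 3.5)/30 = 85% and 435/(31 × 30) = 47%.

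**3. Month missing, literal reading.** The same logic applied to the year leaves 364 - L procedure dates. With mean lag (W + 1)/2, the share is (364 - (W + 1)/2)/365.

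- W = 7: 360/365 = 98.6%
- W = 30: 348.5/365 = 95.5%
- W = 90: 318.5/365 = 87.3%
- W = 182: 272.5/365 = 74.7%
- W = 364: 181.5/365 = 49.7%

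**4. Opposite error.** The rule also pulls later events forward. Enumerating all dates, these are the shares of all events in the window that have true onset after day 30 but an imputed date in days 0-30:
- Day missing: 16.4% for W = 90 and 4.0% for W = 364, against 15.3% and 3.8% moved before the procedure.
- Month missing: 7.8% for W = 364, against 49.7%.

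So with the day missing and onset evenly spread, the 1-month count would hardly change in total, although different events would be counted. It falls when onsets cluster early: if all fall in days 1-7, 83.6% are lost and none are pulled in.

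**5. Alternative reading.** Suppose the first limb means the procedure date whenever the known date parts match the procedure's month or year. Then 0% of post-procedure events move before the procedure, for every W and for either missing part.

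**The case against.** The strongest defence is the first limb. The intake wording looks like leftover drug-trial text, as does the reference to a study drug in section 2.9.5.1. Elsewhere the SAP speaks of RDN or sham as the treatment (sections 2.4 and 2.8). Read for its purpose, the anchor is the procedure date, used when the known date parts allow it, and no event moves. This reading is open, but the text does not state it. A first-day/month fallback needs a known month or year, so the literal split is equally natural: wholly missing dates take the anchor, partial dates take 01. The only intake that the SAP describes is antihypertensive medication (section 2.7.2), which patients were already receiving at entry.

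These objections stand in full:
- Only partial dates in the procedure's own month or year can shift. A day-missing event in a later month never does.
- The number of partial dates is not given and may be small: AEs are asked about at every visit, date of onset is a recorded item, and SAEs were reported within 24 hours of knowledge. A missing month should be rarer than a missing day.
- The creatinine/eGFR criterion for acute renal injury requires a change known to lie within 7 days, so it does not rest on an imputed date.
- AE frequency tables and listings in section 2.9.5.1 have no time filter and lose nothing.

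A reader might infer that the rule certainly moves post-procedure events and so biases the safety comparison in favour of the device. The SAP does not support that. The rule is the same in both arms, so a between-arm distortion needs early partial-dated events to differ by arm, and one available reading moves nothing.

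**Conclusion.** The rule is ambiguous, and its worst-case label is wrong for the fallback in the period closest to the procedure. Taken literally with the day missing, it places before the procedure about 84-85% of events with onset in the first 7 days, 46-47% in the first 30, 15% in the first 90 and 4% over a year. Some later events are pulled into the first 30 days.

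These shares rest on evenly spread procedure and onset dates, apply only to AEs with a partial start date, and become zero under the alternative reading. What is established is a possible understatement of early post-procedure rates in each arm, not a demonstrated safety bias. Severity is low: section 2.4 limits the trial to exploratory and descriptive analysis, and no success criterion depends on the rule.

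**What to change.** In section 2.7.1, replace the treatment-intake anchor and its undefined qualifier with the RDN/sham procedure date, and state:

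*If the known parts of an AE start date are compatible with onset on or after the procedure, and no other data (e.g. end date or visit of first report) show earlier onset, impute the later of the procedure date and the first day of the known month or year. If the whole date is missing, use the procedure date. Otherwise use day 01/month 01.*

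The general 01 rule can stay for other dates. It would also help to report the number of imputed AE start dates per arm, since that number decides whether the point matters at all.

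The cost is a short SAP change and a line of code. A few pre-procedure events may be counted as post-procedure, which is the conservative direction for safety.
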